6.9 FOLLOW UP PROCEDURES

Follow up will consist of 2 parts. To assess for adverse events, approximately 24 ± 6 hours following injection, a follow-up telephone call will be made to the patient, or if the patient chooses another family member who will be able to assess for adverse events. In the event the patient is scheduled to be at the hospital for other testing or appointments, the assessment can also be made in person

Clinical follow-up via chart review will occur to document clinical progression of disease or change in therapy. Follow up chart review to assess for overall treatment response will also be conducted. A chart review will be conducted periodically until recurrence, progression or change in treatment. Data collected from the chart will include office notes from treating physicians, laboratory test results used to determine overall response and radiology reports and images. Response will be determined by the treating physician(s)

7.0 STUDY CALENDAR

	Screening	Baseline	Estradiol Challenge ³	Post Estradiol	Follow-Up
Informed Consent	X				
Standard of Care chart review/Data collection ¹	X				X
Serum Estradiol level blood draw		X	X	X	
¹⁸ F-FFNP -PET/CT Imaging ²		X	X	X	
¹⁸ F-FDG-PET/CT Imaging ⁴	X				

1. Chart review/ data collection consists of obtaining source documents for eligibility check at screening and records pertaining to eligibility and treatment response as specified in section 6.6 at follow-up time point(s)
2. FFNP-PET/CT imaging one 2 separate occasions as described in section 6.0-6.2 of protocol and follow up for adverse events as described in section 6.7
3. Estradiol challenge ¹⁸F-FFNP-PET/CT imaging can be completed as soon as the following day as described in section 5.3. A maximum of 4 weeks is allowed between the baseline and estradiol challenge scans
4. If performed, FDG-PET/CT imaging must be done on day separate from FFNP-PET/CT. Preference is for FDG to be scanned prior to FFNP but alternative scheduling options may be necessary

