Because the mechanisms of action of these new endocrine therapy agents are different than that of tamoxifen, they do not typically cause clinical flare. Accordingly, we investigated the induction of a “metabolic flare reaction” using a brief treatment with estradiol, a more potent estrogen than tamoxifen, seeking to find a more robust response. Once again, we found that both baseline tumor FES uptake and metabolic flare, assessed by serial FDG-PET, after a 1-day estradiol challenge, were predictive of responsiveness to endocrine therapy in ER+ breast cancer (Dehdashti F. *Breast Cancer Res Treat.* 2009 Feb;113(3):509-17). We found that with an increase in tumor FDG uptake $\geq 12\%$ as the criterion for defining estradiol-induced metabolic flare based on ROC curve analysis, the PPV for response to endocrine therapy was 100% (all 15 of such patients responded) and the NPV was 94% (only 2 of 36 such patients responded). The baseline FES uptake (using a cutoff SUV of ≥ 2 as the criterion for defining functional ER based on our prior experience) had PPV and NPV for response to therapy of 50% (12 of 24 FES+ patients responded) and 81% (5 of 27 FES- patients responded), respectively. Thus, metabolic flare assessed by FDG-PET was again a stronger predictor of response to ET than a direct measure of ER level by FES-PET.

Subsequently, we studied another group of patients with hormone-sensitive metastatic breast cancer treated with an AI, with at least 24 weeks of progression-free survival, or relapse after two or more years of adjuvant AI, again using serial FDG-PET and estradiol challenge. An estradiol stimulated increase in FDG uptake of $\geq 12\%$ (prospectively defined from the prior study) was predictive of response (PPV of 80%; 95% CI: 61%–92%). (Ellis MJ. *JAMA* 2009 Aug 19;302(7):774-80). This compares with PPV of 100% on the prior study.

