2.0 OBJECTIVES

Our hypothesis is that change in ¹⁸F-FFNP uptake following 1-day of estradiol is a strong predictor of response to ET in patients with hormone-sensitive (ER⁺/± PgR⁺)/HER2- breast cancer. We believe the increase in tumor PgR after 1-day estradiol will be more reliable than a decrease after estrogen deprivation, particularly because most breast cancer patients are postmenopausal and basal PgR levels will be low due to the low endogenous, menopausal estrogen levels. Thus, we propose to use a hormone-challenge test for assessment of functional

ER based on the change in ^{18}F -FFNP uptake before and after a 1-day estradiol challenge in patients with ER+ metastatic breast cancer. We expect that the changes in ^{18}F -FFNP uptake to be a highly reliable means to predict a favorable response of ER+ breast cancer to ET. We propose to study patients with biopsy-proven new diagnosis of ER+ metastatic/recurrent breast cancer who are going to be treated with ET (tamoxifen, AI agents or faslodex) according to standard of care.

2.1. Evaluate whether the change in tumor uptake of ^{18}F -FFNP following a 1-day estradiol challenge differs among patients who respond to ET versus those who do not respond.

2.1.1 Determine the optimum cutoff value for change in tumor ^{18}F -FFNP uptake after estradiol to distinguish responders from nonresponders.

2.1.2 Evaluate whether the change in tumor uptake of FFNP can identify patients with hormone-sensitive disease who will respond to ET with greater sensitivity and selectivity than tumor PgR measured by IHC.

2.2 Evaluate the heterogeneity of tumor ^{18}F -FFNP uptake at baseline and after estradiol challenge in patients with multiple metastatic foci.

2.2.1. Explore whether response is related to ^{18}F -FFNP uptake heterogeneity. To assess the heterogeneity at the baseline, a comparison with FDG-PET/CT will be performed to map the metabolically active disease. Once the metabolically active disease is determined, FDG+/FFNP- will be considered as discordant lesions. At follow-up, the baseline FFNP-PET/CT will be correlated with follow-up FFNP-PET/CT to assess heterogeneity in response to estradiol.

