5.2 Patient Population

Fifty postmenopausal women OR Pre-menopausal for whom standard ET is planned with ovarian suppression (imaging on study should be completed prior to start of ovarian suppression) with newly diagnosed, metastatic or recurrent breast cancer which is ER+ disease (ER+/PgR+/HER2-, ER+/PgR-/HER2-) will undergo one FDG PET/CT scan to map the metabolically active disease plus two ^{18}F -FFNP-PET/CT; one prior to estradiol challenge test and a second one immediately following one day of estradiol challenge test (2 mg tid). All scans will be completed prior to the start of standard of care ET. Patients who have had an FDG-PET/CT scan (or other functional studies such as bone scan in patients with bone dominant disease or a contrast CT scan for hepatic dominant disease) done within 8 weeks of study entry may not need to repeat the scan at the discretion of the Principal Investigator and Co-Investigator Medical oncologists. Any subject whose imaging is deemed not evaluable for any reason or any subject who does not complete both FFNP-PET/CT imaging sessions for any reason may be replaced on study. The study ID assigned to the subject being replaced will not be re-used.

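### The FDG map that defines baseline discordance in objective 2.2.1 need not precede estradiol and may be a bone scan or CT, which could bias or leave undefined this exploratory analysis

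*Combined protocol and SAP*

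**What the plan says.** Section 2.0, objective 2.2.1, explores whether response is related to heterogeneity of FFNP uptake. It fixes the role of FDG: "To assess the heterogeneity at the baseline, a comparison with FDG-PET/CT will be performed to map the metabolically active disease". It then gives the rule: "FDG+/FFNP- will be considered as discordant lesions".

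Three places govern when, and whether, FDG is done:

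- The Section 7.0 calendar marks FDG under Screening only. Its footnote 4 requires a different day from FFNP and adds: "Preference is for FDG to be scanned prior to FFNP but alternative scheduling options may be necessary".
- Section 5.2 sets one further limit: "All scans will be completed prior to the start of standard of care ET". It does not mention estradiol.
- Section 5.2 also accepts, within 8 weeks of study entry, an existing FDG scan or "other functional studies such as bone scan in patients with bone dominant disease or a contrast CT scan for hepatic dominant disease". Such patients "may not need to repeat the scan at the discretion of the Principal Investigator and Co-Investigator Medical oncologists".

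Section 5.3 lets the first estradiol dose follow the baseline FFNP session at once, with the repeat FFNP session the next day and at most 4 weeks between the two sessions.

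**The concern.** A map meant to describe disease at baseline should be acquired before anything that alters the signal being mapped. Section 1.3 reports that one day of estradiol raises tumour FDG uptake, and that this rise goes with response to endocrine therapy. If some research FDG scans follow estradiol, classification of a lesion as FDG-positive depends partly on the outcome to which objective 2.2.1 relates it.

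Substitution is a separate problem and does not depend on flare. A bone scan or contrast CT gives no FDG status, and the plan has no alternative rule for those patients. They could be dropped, counted as concordant or classified in some other way. Because substitution follows the dominant site of disease, the gap is not random across patients.

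**Working it through.** **1. Is FDG after estradiol permitted?** Footnote 4 states a preference about order relative to FFNP and a separate-day rule. Section 5.2 requires only that scans precede endocrine therapy. No section requires FDG before the first estradiol dose. On the fastest Section 5.3 schedule, estradiol starts straight after baseline FFNP. An FDG scan not already done cannot share that day, so it must follow estradiol. The Screening column points the other way, so the table and its footnote need reconciling.

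**2. The protocol's own figures, reproduced.** In the first estradiol-challenge study in Section 1.3, all 15 patients with a rise of at least 12% responded, and 2 of 36 without it responded.

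- PPV = 15/15 = 100%. NPV = (36 − 2)/36 = 34/36 = 94%. Both match the text.
- The FES counts for the same study give the same margins: 24 + 27 = 51 = 15 + 36 patients, and 12 + 5 = 17 = 15 + 2 responders.

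**3. The same counts by response group.**

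| | Rise ≥ 12% | No such rise | Total |
|---|---|---|---|
| Responders | 15 | 2 | 17 |
| Non-responders | 0 | 34 | 34 |

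Responders: 15/17 = 88% (exact 95% CI 64% to 99%). Non-responders: 0/34 (exact 95% CI 0% to 10%). The 12% cutoff was chosen by ROC analysis, so this separation is probably optimistic. In the second study, with the cutoff fixed in advance, PPV was 80% (95% CI 61% to 92%), so about 20% of patients with the rise did not respond.

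**4. Which lesions could change status?** With a fixed positivity cutoff, a lesion switches if its pre-estradiol SUV is at least cutoff/(1 + rise). For a 12% rise this is 1/1.12 = 89% of the cutoff. For a 40% rise, a level that Section 1.3 says was rarely exceeded, it is 1/1.40 = 71%. Only lesions just below the cutoff are at risk.

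**5. How many might switch? An illustration only.** The inputs below are assumptions and are not in the documents. Take lesion SUV as lognormal with a fixed cutoff, median m times the cutoff, log-SD s, and rise factor f. The share switching is Φ((ln m + ln f)/s) − Φ(ln m/s).

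| m | s | FDG-positive before | Switch, f = 1.12 | Switch, f = 1.40 |
|---|---|---|---|---|
| 1.5 | 0.5 | 79.1% | 5.9% | 14.0% |
| 1.5 | 0.7 | 71.9% | 5.2% | 13.7% |
| 2 | 0.5 | 91.7% | 2.9% | 6.3% |
| 2 | 0.7 | 83.9% | 3.6% | 9.0% |
| 3 | 0.5 | 98.6% | 0.6% | 1.2% |
| 3 | 0.7 | 94.2% | 1.7% | 3.8% |

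Alternatively, fix the FDG-negative share at 20% and take log-SD 0.4 to 0.6. After the rise, the share is Φ(z(0.20) − ln f/SD): 13.0% to 15.1% for a 12% rise and 4.6% to 8.0% for a 40% rise. That is 4.9 to 7.0 and 12.0 to 15.4 percentage points switching.

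These shares apply to lesions that flare in patients scanned after estradiol. A switched lesion becomes discordant only if it is also FFNP-negative. The count of discordant lesions can then only rise, but a proportion taken among FDG-positive lesions could move either way.

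**6. What does not use FDG.** The Section 10.1 comparison of FFNP change, the PPV/NPV and the power statement do not use it. The power statement reproduces with a two-sided t-test: 1.01 SD for 10 versus 40 and 0.809 SD for 25 versus 25.

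**The case against.** The strongest reply is that the plan intends a pre-estradiol scan. The calendar puts FDG at Screening, objective 2.2.1 speaks of baseline, and a prior scan accepted under Section 5.2 would normally precede estradiol. Footnote 4 never mentions estradiol, and an FDG scan between baseline FFNP and the first dose also satisfies it. This stands as a statement of intent, but the text still permits the late scan. A reader might infer that post-estradiol FDG is planned or common; the documents do not say so.

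A reader might also infer that estradiol raises FDG by at least 12% in every responder and leaves non-responders untouched. Section 1.3 does not support that: 12% is a cutoff, 2 of 17 responders fell below it, and the second study's PPV was 80%.

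Nor are the switching shares estimates of bias. Section 6.5 has FDG read by standard-of-care procedures, with no SUV cutoff. The duration of the rise and the number of late scans are not given, and the rise is described as modest.

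Substitution is a limited choice, confined by site, time window and investigator discretion. That limits how often discordance is undefined, but it does not supply a rule for those patients. Finally, Section 6.5 measures FFNP SUVmax and T/N across lesions without FDG, so heterogeneity can still be studied.

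**Conclusion.** The concern holds for the FDG-based discordance analysis in objective 2.2.1. The plan allows the baseline map to be acquired after estradiol, and its own data (15 of 17 responders against 0 of 34 non-responders) indicate that such a map would be altered mainly in responders. The relation between discordance and response could be biased through lesions near the positivity threshold. The size cannot be determined. Under the stated assumptions, about 0.6% to 7% of affected patients' lesions would switch with a 12% rise and about 1% to 15% with a 40% rise, before allowing for the unknown share scanned late. In patients with a bone scan or CT instead of FDG, discordance cannot be formed as defined, whatever the size of any flare.

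The wider inference that the trial's main result is compromised is not supported. Objective 2.2.1 is exploratory, and the primary FFNP comparison, PPV/NPV, power and FFNP-only heterogeneity measures are unaffected. This is a cheap improvement worth making.

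**What to change.** - Reconcile footnote 4 with the Screening column, so that a research FDG scan is acquired before the first estradiol dose. It may still follow the baseline FFNP scan, on a separate day and within the 4 weeks that Section 5.3 allows between FFNP sessions.
- Record for each patient the modality used as the map and its date and time relative to the first estradiol dose.
- Add to Section 10.1 that the FDG-positive/FFNP-negative analysis uses pre-estradiol FDG-PET/CT only. Report patients with post-estradiol FDG, and patients with a bone scan or CT substitute, separately and outside the discordance rate.

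The cost is a smaller set for an exploratory aim. Patients without FDG before baseline FFNP also lose the option of a repeat FFNP scan the next day. The sample size and the estradiol challenge itself do not change. For scans already done, only the recording and analysis-set steps apply.

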7.1 Data Submission Schedule

Case report forms with appropriate source documentation will be completed according to the schedule listed in this section.

Case Report Form	Submission Schedule
Original Consent Form	Prior to registration
Eligibility Form	Prior to baseline imaging session
PET Imaging Form	At time of each imaging session
PET Image Analysis	Approximately 24 weeks after estradiol FFNP-PET/CT challenge scan

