6.5 Image Analysis

The emission images will be corrected for measured attenuation using CT data according to the provide scanner manufacturer software package. FDG-PET/CT images will be evaluated and reported according to standard of care imaging procedures.

FFNP-PET/CT images will be evaluated by one observer qualitatively. PET images also will be evaluated semiquantitatively with the knowledge of the location of the lesion(s) by the use of the standardized uptake value (SUV) and tumor-to-normal tissue (T/N)

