ratio. The SUV is widely used for assessment of regional tracer accumulation in oncological studies, is technically simple to perform, and makes imaging easier for the patient because longer dynamic imaging is not required. SUV is a decay-corrected measurement of activity per volume of tissue (nCi/mL) divided by the average activity per unit mass in the entire body. The absolute change and the percent change in uptake of ^{18}F -FFNP will be assessed semiquantitatively and correlated with the clinical and radiologic results and subsequently with the results of the clinical follow-up evaluation. In patients with multiple lesions, the uptake up to 5 most intense lesions seen on PET images will be determined and the overall average values for all of the known lesions also will be recorded. The changes in SUV and T/N between the baseline and post estradiol challenge FFNP-PET/CT images will be compared in responders and nonresponders. Volumes of interest (VOIs) will be drawn around the entire lesion with the knowledge of the location of the tumor. SUV_{max} will be determined within the VOI. In addition, a similar volume of interest will be drawn in a comparable normal tissue region. The T/N ratio will be calculated by dividing the SUV_{max} of the tumor by the average SUV of normal comparable tissue. The absolute change and the percent change in uptake of ^{18}F -FFNP will be assessed semi-quantitatively and correlated with the clinical and radiologic results and subsequently with the results of the clinical follow-up evaluation. In patients with multiple lesions, the uptake of up to 5 lesions, selected as the most intense lesions seen on PET, will be determined and the overall average values for all of the known lesions also will be recorded. In addition, in patients with multiple lesions, SUV_{max} and T/N ratio will be measured for all known measurable lesions to assess within-patient heterogeneity in ^{18}F -FFNP uptake. Considering the optimum cutoff value for ^{18}F -FFNP uptake that distinguishes responders from nonresponders, lesions will be classified as ^{18}F -FFNP+ for lesions with ^{18}F -FFNP uptake at or greater than the cutoff value and ^{18}F -FFNP- for lesions with ^{18}F -FFNP uptake below the cutoff value. The changes in SUV and T/N after treatment will be compared in responders and nonresponders. The results of the PET studies will not be provided to the patient or the treating oncologist (see above). Clinical follow-up will provide information on tumor response, which will then be correlated with the sequential PET results to determine if these are predictive of ultimate response to estrogen therapy.

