6.8 Evaluation of Tumor Response

The patients will be followed by their treating oncologist every 3 months per standard of care scheduling and not dictated by protocol (or earlier in case of a suspicion of early progression) until disease progression. Clinical benefit (complete response + partial response + stable disease) will be determined ≥ 6 months after initiation of therapy. Response will be evaluated according to RECIST 1.1 (Eisenhauer EA, Therasse P, Bogaerts J, et al. New response evaluation criteria in solid tumors: Revised RECIST guideline (version 1.1). *Eur J Cancer* 2009; 45:228-47). This evaluation will be based on the composite results of imaging studies (CT, MRI, bone scintigraphy, FDG-PET, etc.), serum tumor markers and evaluation of symptoms as deemed appropriate by the treating physician at the 6-month visit or at the time that there is evidence of clinical progression of disease, if before six months. Clinical response using RECIST version 1.1 by an oncologist will be defined as:

6.7.1 Complete Response:

Disappearance of all target lesions: Disappearance of all target lesions. Any pathological lymph nodes (whether target or non-target) must have reduction in short axis to <10 mm.

6.7.2 Partial Response (PR):

At least a 30% decrease in the sum of the longest diameter (LD) of target lesions taking as reference the baseline sum LD.

6.7.3 Progression (PD):

At least a 20% increase in the sum of the LD of target lesions taking as references the smallest sum LD recorded since the treatment started or the appearance of one or more new lesions.

6.7.4 Stable Disease (SD):

Neither sufficient shrinkage to qualify for PR nor sufficient increase to qualify for PD taking as references the smallest sum LD since the treatment started. Patients having a documented response with no reconfirmation of the response will be listed with stable disease.

6.7.5 Osseous disease only or osseous-dominant disease:

For patients with osseous metastasis only, a complete response was defined as disappearance of all objective and clinical disease, including complete normalization of radiological studies and tumor markers. A partial response was defined as a decrease in pain with evidence of recalcification of known osseous lesions on radiography. Disease progression was defined as worsening of disease on nuclear medicine scan or radiographs or worsening of pain and decline in

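### The FFNP image analysis form is due about 24 weeks after the challenge scan, when early progression may be known, and the plan neither masks the reader to outcome nor locks the measurements first

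*Combined protocol and SAP*

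**What the plan says.** - **When the analysis form is due.** Section 7.1 sets the rule "Case report forms with appropriate source documentation will be completed according to the schedule listed in this section". The PET imaging form is due at each session. The separate PET Image Analysis form is due "Approximately 24 weeks after estradiol FFNP-PET/CT challenge scan". No other section gives a time for the analysis.
- **Who reads, and how.** Section 6.5 says "FFNP-PET/CT images will be evaluated by one observer qualitatively". A separate sentence introduces the semiquantitative SUV and T/N evaluation. It gives no number of readers, and the only knowledge it grants them is lesion location. In the drawn volume of interest (VOI), "SUV_{max} will be determined within the VOI". The T/N denominator is the mean SUV of a normal region that the reader picks as comparable. With several lesions, "the uptake of up to 5 lesions, selected as the most intense lesions seen on PET, will be determined", and an average over all known lesions is also recorded.
- **When the outcome is known.** Under Section 6.8, clinical benefit is judged at 6 months or more after ET starts, or "at the time that there is evidence of clinical progression of disease, if before six months". Visits are every 3 months, or sooner if progression is suspected. Section 3.1 also admits neoadjuvant patients with any length of ET if surgery will supply the response assessment.
- **What is masked.** Sections 6.0 and 6.5 keep the PET results from the treating oncologist, apart from an unexpected life-threatening CT finding. Section 6.9 leaves the assessment of response to the treating physician. No section addresses masking in the other direction, from outcome to FFNP reader.

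**The concern.** The study asks whether the FFNP change predicts response, so the FFNP measurement has to be made independently of response. The plan protects one side: the person judging response does not see the FFNP result. It leaves the other side open. Under Section 6.9, chart review brings office notes, radiology reports and follow-up images into the study while the analysis form is still pending.

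A reader who knows that a patient has progressed can, without intending to, choose different lesions, a different normal region, or a different qualitative score. The natural direction is a smaller uptake change in non-responders, which favours the hypothesis. The Wilcoxon comparison, the ROC cutoff, and the PPV and NPV in Section 10.1 all use these readings. The cutoff is meant for future prediction, so any bias would be carried forward with it.

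**Working it through.** **1. The plan's own figures.** Section 10.1 gives detectable differences of 101% SD (10 versus 40) and 80.9% SD (25 versus 25), at 80% power and two-sided 0.05. With the noncentral t on 48 degrees of freedom and noncentrality d × √(n1·n2/(n1+n2)):
- 10 versus 40: √(400/50) = 2.828; solving for 80% power gives d = 1.011.
- 25 versus 25: √(625/50) = 3.536; solving gives d = 0.809.

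Both figures reproduce. They assume unbiased measurement, and masking changes no sample size.

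**2. Timeline, counted from the post-estradiol scan.** Section 5.2 puts all scans before ET. Let ET start g weeks after the scan, with g ≥ 0; the plan sets no upper limit for g.
- Analysis form: about week 24.
- 3-month visit: 365.25/4/7 = 13.0, so week 13 + g. This precedes week 24 whenever g is below about 11.
- 6-month assessment: 365.25/2/7 = 26.1, so week 26.1 + g, at least about 2 weeks after the form date.

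So at week 24 the planned 6-month response is normally not yet on record. Progression found at or before the 3-month visit normally is, and so may be the outcome after early surgery. The documents give no distribution of progression times, so the share of non-responders known at week 24 cannot be derived.

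**3. Where judgement enters.** SUVmax is a single-voxel maximum and is insensitive to small shifts of the VOI border, so reader influence on it is limited once the lesion is chosen. More room is left in the qualitative read, in which lesions are taken, in the undated set of known lesions, and in the normal region for T/N. T/N is one of the primary endpoint measures in Section 10.1.

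**4. Illustration of size.** The assumptions are not from the documents: no true difference, normally distributed changes, and the reader lowers the measured change by b SD in a share f of non-responders. Two-sided Wilcoxon at 0.05, 20,000 simulated trials per setting. Rejection rates:

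| Responders vs non-responders | f | b = 0 | b = 0.2 | b = 0.3 | b = 0.5 |
|---|---|---|---|---|---|
| 10 vs 40 | half | 4.5% | 5.2% | 6.3% | 9.3% |
| 25 vs 25 | half (12 of 25) | 5.0% | 6.0% | 6.8% | 11.9% |
| 10 vs 40 | all | 4.7% | 7.9% | 12.1% | 26.1% |
| 25 vs 25 | all | 4.5% | 9.7% | 16.6% | 38.0% |

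The spurious ROC area is about 0.53, 0.54 and 0.57 for f of one half, and 0.56, 0.58 and 0.64 for all. A closed form agrees: area = (1 − f) × 0.5 + f × Φ(b/√2). For f = 0.5 and b = 0.5 this is 0.25 + 0.5 × 0.638 = 0.569.

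The rows for all non-responders are an upper bound for each b. They would require every progression to be known at the read, including those first found at the 6-month visit, which step 2 makes unlikely.

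**The case against.** The following can be said for the plan.

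- **A form date is not a read date.** This is correct: the images could be read on the day of the scan. Section 6.5 also describes the uptake change as "correlated with the clinical and radiologic results and subsequently with the results of the clinical follow-up evaluation", which suggests that the PET measure comes first. But it describes an order and does not require one. A team that reads at week 24 with progression known is fully compliant.
- **Silence is not unmasking.** A reader might infer from Section 7.1 that the FFNP reader knows the outcome. The documents do not say so; they are silent. The supportable statement is that masking is not specified.
- **The single observer belongs to the qualitative read.** It is tempting to conclude that one person makes every choice behind the primary endpoint. Section 6.5 does not state how many people make the SUV and T/N measurements.
- **Most outcomes are still open at week 24.** A reader might infer that most non-responders are known by then. The planned assessment falls after the form date, chart review is only periodic, and no progression times are given. Exposure is mainly to early progressors and early surgery.
- **The measurement is rule-bound.** Whole-lesion VOIs, SUVmax and the most-intense-lesion rule do narrow discretion. They do not remove it, least of all for T/N.
- **This is a pilot.** True, but the cutoff is its main product and the protection costs almost nothing.

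These points limit the claim. They leave the gap in place, whatever the form date.

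**Conclusion.** The point holds as a gap in protection and does not show that bias occurred. The only scheduled time for the FFNP analysis falls after early progression can be known, and nothing masks the reader(s) or locks the readings. The plan's masking runs only from PET to oncologist.

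The size of any bias cannot be derived. Under an assumed shift of 0.2 to 0.5 SD in half of the non-responders, type I error is about 5 to 9% (10 versus 40) or 6 to 12% (25 versus 25). At the low end that is little or no inflation. The 26% and 38% figures should not be cited as expected values. The reading also takes non-response to mean progression, as the clinical-benefit definition in Section 6.8 implies; Section 10.1 does not define it. The change should be made because it is cheap and guards every predictive result.

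**What to change.** - **Section 6.5:** state that whoever makes the qualitative and semiquantitative FFNP reads has no access to follow-up or response data.
- **Section 7.1:** make lesion selection, raw SUV and T/N due and locked soon after the second FFNP scan, for example within 4 weeks, and before any outcome data are opened. A later batch read is an acceptable alternative if it is masked.
- **Lesion classification:** Section 6.5 labels lesions FFNP-positive or FFNP-negative by the cutoff that separates responders from non-responders. This needs outcome data, so do it afterwards from the locked values.
- **Reads already made with the outcome known:** redo them masked, or exclude them in a sensitivity analysis.

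The cost is a few sentences and a changed due date. Scans, sample size and patient care stay the same. The small downside is that reads must be done promptly, or batched under masking, rather than at leisure at the end of follow-up.
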